### 8.4.3 Electrocardiograms

Subjects will be supine in a rested and calm state for at least 5 minutes before the ECG assessment is performed. ECG machines and Holter/telemetry will be provided by an ECG core lab, and these provided machines must be used for all study-related ECG requirements. Please note, in the event the provided 12-lead ECG machine (provided by the ECG core lab) is not functioning, the sites may utilize their own ECG machines and follow-up with the ECG core lab for uploading instructions. HR, QRS, QT, QTc, and PR intervals will be reported by the core lab.

Resting 12-lead ECGs will be recorded at the timepoints outlined in Table 8-1. On VP-315 dosing days, 5-electrode Holter/telemetry will also be monitored continuously starting 15 minutes prior to injection and 2 hours after the last injection of the day. For subjects in Part 2 Cohorts 4 and 5 expansion groups, Holter/telemetry has been decreased to 1-hour after the last injection of the day after receipt of the second daily dose of VP-315 (an additional hour may be continued at the discretion of the PI).

If a change in rhythm is detected during monitoring, the investigator will be notified by the central ECG core lab for evaluation of potential adverse events.

## 8.4.4 Clinical Laboratory Testing

A Clinical Laboratory Improvement Amendments (CLIA) certified [either central or local] laboratory will perform the clinical laboratory tests for this study as scheduled in Table 8-1. Tests are listed in Table 8-2 and will be performed at Screening, at each Safety Assessment Visit, at Unscheduled Visits and at the EOS; for subjects with excised lesions on both the face and the body, clinical laboratory samples will be collected only at the second EOS visit (i.e, at the EOS for Body).

Table 8-1 Clinical Laboratory Tests

Clinical Laboratory Tests	
Hematology:	Serum Chemistry:
Red Blood Cell Count (RBC)	Blood Urea Nitrogen (BUN)
White Blood Cell Count (WBC) w/ differential (absolute)	Creatinine
Hematocrit	SGOT (AST)
Hemoglobin	SGPT (ALT)
Mean Corpuscular Volume (MCV)	Lactic Dehydrogenase (LDH)
Mean Corpuscular Hemoglobin Concentration (MCHC)	Alkaline Phosphatase (ALP)
Platelet Count	Total Bilirubin
	Total Protein
	Albumin
	Glucose
	Calcium
	Sodium
	Chloride
	Potassium
	Bicarbonate
Pregnancy Test: (Only on subjects of childbearing potential)	Serum tryptase
Serum β-hCG (Screening, Safety Assessment Visits, and EOS)	
Urine (prior to injection on Day 1 of each week)	
T-Cell Clonality (Central lab only)	Expansion Cohorts 4 and 5
	Serum Pharmacokinetics (PK) [Central lab only]

EOS=end of study (visit); EOT=end of treatment (visit)

## 8.4.5 Serum Tryptase Assessment

Blood samples for serum tryptase assessments will be collected at screening; additional samples will be taken as necessary to monitor hypersensitivity reactions.

Blood samples will be collected in accordance with the National Institute for Health and Care Excellence clinical guideline 134 when any hypersensitivity reaction occurs (e.g., as soon as possible following the occurrence of a hypersensitivity reaction, and again 60 to 120 minutes

later). The actual collection time must be entered into the subject's record/source and transcribed accordingly.

### 8.4.6 Cutaneous Reaction Assessment

A CRA will be performed prior to injection at all visits after W1D1 (Appendix 1); the evaluation results are required for the evaluation of necrosis and DLTs. These local skin reactions will be collected independently of the adverse reactions to provide information on the specific types of reactions that can be expected to occur.

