#### **8.2** Treatment Period

After completion of screening/baseline assessments (Table 8-1), subjects will be enrolled to receive intratumoral VP-315. In Part 1, each 7-day treatment week comprises up to 3 consecutive treatment days followed by a no-treatment period of at least 4 days. Once a target lesion has necrosed, treatment of that lesion stops, and treatment of subsequent target lesions may continue on Day 1 of the following week. Subjects may be treated for a maximum of 2 treatment weeks. In Part 2 of the study, each 7-day treatment week comprises up to 2 or 3 consecutive treatment days followed by a no-treatment period of at least 4 days.

After each treatment, all subjects in Part 1, Part 2 – Cohort 1, Cohort 2 and Cohorts 4 and 5 (first 10 subjects in each) will remain in the study center for up to 2 hours for safety monitoring (e.g., continuous blood pressure, electrocardiographic and AE monitoring) After each treatment, the additional 20 subjects enrolled into Cohort 4 and 5 expansion groups: will remain in the study center for up to 1-hour (reduced from 2-hours) post second injection for safety monitoring (e.g., continuous blood pressure, electrocardiographic and AE monitoring), an additional hour may be continued at the discretion of the PI. Plasma PK sampling will be collected (in Part 2, Cohorts 4 and 5 expansion groups) as detailed in Table 8-1.

The subject will return to the clinic the day after treatment for assessment by the investigator. The treatment site will be photographed and assessed for CRA (Appendix 1) and PGA of response to treatment (Appendix 2), with images uploaded for real-time assessment by the SRC (Part 1) and/or Medical Monitor (Part 2). The CRA and PGA will be performed by the investigator or trained personnel at each treatment visit, at the EOT visit, and at the EOS visit.

Subjects in Part 2 (Cohorts 4 and 5) with only 1 target lesion, that complete week one of treatment and the W1 safety assessment visit without complete necrosis should return for a Limited Safety Assessment Visit on W2D1 for further evaluation of the lesion for necrosis.

Subjects that complete two weeks of treatment and the W2 safety assessment visit without complete necrosis should return for a Limited Safety Assessment Visit on W3D1.

Nontarget BCC lesions will be observed for abscopal effect.

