- h. Blood samples for serum tryptase assessments will be collected at screening; additional samples will be collected as soon as possible following the occurrence of a hypersensitivity reaction, and again 60 to 120 minutes later.
- i. Serum pregnancy test will be performed only on subjects of *childbearing potential* at all visits where other clinical laboratory tests are collected and at the EOS visit, prior to the subject being discharged from the study (Note: for subjects with excised lesions on both the face and the body, clinical laboratory samples and the serum pregnancy testing will be collected only at the second EOS visit [i.e., at the EOS for Body; 2 weeks after excision]).
- i. Blood collected on a subset of subjects at screening and EOT visits. Approximately 3.0 mL will be collected in BD VacutainerTM tubes with K2EDTA.
- k. Urine pregnancy test will be performed prior to injection on Day 1 of each week only on subjects of childbearing potential.
- 1. If an eligible, *HISTORICAL* biopsy (shave or punch biopsy sample taken within 90 days prior to the W1D1 visit) is available in advance of subject screening, slides are to be submitted to the central dermatopathologist in accordance with the laboratory manual. If the subject has no *HISTORICAL* biopsy, shave or punch biopsy of the suspected BCC must be performed within t 90 days of W1D1. Shave biopsies will be performed according to standard of care to include superficial or middle papillary dermis. For punch biopsies,

- a 2-mm biopsy will be collected for suspected BCC ≥0.5 cm to 1.0 cm, and 3-mm punch biopsy for suspected BCC >1.0 cm to 2.0 cm. Up to 5 suspected lesions may be biopsied. Punch biopsy sites should be closed with 1 to 2 non-absorbable sutures (sized 40 or 50) depending on investigator preference.
- m. Physician's Global Assessment and Cutaneous Reaction Assessment will be performed prior to injection at all visits after Week 1 Day 1 for subjects in all parts of the study. The results of the Cutaneous Reaction Assessment are required in Parts 1 and 2 for evaluation of necrosis and DLTs.
- n. Subjects will return for Follow-up Visits approximately 28-42 days (4-6 weeks) for Part 1 and 84-91 days (12 to 14 weeks) for Part 2 after receipt of first dose of VP-315 for excision of all BCC lesions (EOT).

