### 8.5.2 Lesion Photography

Prior to each treatment, each safety visit, prior to excision and EOS, the treatment site, as well as any additional non-treated lesions that are to be followed, will be photographed, and assessed for the CRA. Site(s) will be provided with specialized equipment and training for consistent quality photographs. Photographs may be collected and stored on digital media.

Custom photographic equipment will be manufactured by Canfield for use in this study. Canfield will provide each site with a laptop computer with Canfield's proprietary Canfield Capture pre-installed on the equipment to guide site staff through all of steps of the image capture process required for this study. The software will be configured to include the specific visit schedule, image views and lighting modes to satisfy the needs of the study. In order to ensure consistent serial clinical photography is achieved during this study, all subject photographs will be reviewed (monitored) on an ongoing basis. Digital images will be transferred to Canfield via the secure website.

All images will be monitored for technical adherence to photographic protocol. Subject information, including site number, subject ID number, subject initials, and session date, will be entered into the database. The subject's F/U images will be technically reviewed compared to the baseline images. Photographic documentation will be carefully monitored to

assure that consistent serial photography will be achieved. Any subject images received that show identifying features (as defined by the Sponsor) will be digitally modified in an effort to protect the subject's identity. Image masking will occur where applicable during the monitoring process and a quality check will be completed before the images are available to view, download and print.

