# 15. APPENDICES

# Appendix 1 Cutaneous Reaction Assessment\*

Evaluate the tissue condition at the treatment site for the presence and severity of each of the following cutaneous reactions.

	Target Lesions		Nontarget Lesions		
Reaction	Lesion 1	Lesion 2	Lesion 1	Lesion 2	Lesion 3
Erythema	□ none	□ none	none	□ none	□ none
	□ mild	☐ mild	□ mild	☐ mild	☐ mild
	☐ moderate	☐ moderate	☐ moderate	☐ moderate	☐ moderate
	□ severe	severe	□ severe	□ severe	□ severe
Induration	none	□ none	none	□ none	□ none
	$\square$ mild	☐ mild	$\square$ mild	☐ mild	☐ mild
	☐ moderate	☐ moderate	$\square$ moderate	☐ moderate	☐ moderate
	□ severe	□ severe	□ severe	□ severe	□ severe
Swelling	none	□ none	none	□ none	□ none
	☐ mild	☐ mild	□ mild	☐ mild	☐ mild
	☐ moderate	☐ moderate	☐ moderate	☐ moderate	☐ moderate
	□ severe	□ severe	□ severe	□ severe	□ severe
Blister	□ none	□ none	□ none	□ none	□ none
Formation	□ mild	☐ mild	$\square$ mild	☐ mild	□ mild
	☐ moderate	☐ moderate	☐ moderate	☐ moderate	☐ moderate
	□ severe	□ severe	□ severe	□ severe	□ severe
Desquamation	□ none	□ none	□ none	□ none	□ none
	□ mild	☐ mild	$\square$ mild	☐ mild	□ mild
	☐ moderate	☐ moderate	☐ moderate	☐ moderate	☐ moderate
	□ severe	□ severe	□ severe	□ severe	□ severe

Evaluate the tissue condition at the treatment site for the presence and severity of each of the following cutaneous reactions.

	Target Lesions		Nontarget Lesions		
Reaction	Lesion 1	Lesion 2	Lesion 1	Lesion 2	Lesion 3
Erosion	□ none	□ none	□ none	□ none	□ none
	☐ mild	☐ mild	☐ mild	☐ mild	☐ mild
	☐ moderate	☐ moderate	☐ moderate	☐ moderate	☐ moderate
	□ severe	□ severe	□ severe	□ severe	□ severe
Ulceration	□ none	□ none	□ none	□ none	□ none
	☐ mild	☐ mild	☐ mild	☐ mild	□ mild
	☐ moderate	☐ moderate	☐ moderate	☐ moderate	☐ moderate
	□ severe	□ severe	□ severe	□ severe	□ severe
Necrosis	□ none	□ none	□ none	□ none	□ none
	☐ mild	☐ mild	☐ mild	☐ mild	☐ mild
	☐ moderate	☐ moderate	☐ moderate	☐ moderate	☐ moderate
	□ severe	□ severe	□ severe	□ severe	□ severe

\*Complete the assessment for each reaction and for any reaction that is Mild, Moderate or Severe enter event on the Adverse Event Page

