## 2. Objectives and Endpoints

The following objectives and endpoints will be considered.

Part 1	
Primary Objectives	Endpoints

 
To assess the safety, tolerability, and maximum tolerated dose (MTD) of ascending dose strengths of VP-315
 
	
 
Discontinuations due to adverse events (AEs); occurrence of dose-limiting toxicities (DLTs)
 
Cutaneous Reaction Assessment (CRA)
 

Exploratory Objectives 
 
To evaluate the objective antitumor efficacy of VP-315
 
	
 
Histological clearance of treated lesion(s) at excision
 
Clinical clearance of treated lesion(s) as determined by visual assessment (no tumor seen upon visible inspection) at excision
 
Estimate of remaining tumor volume (necrotic cells:tumor cells) at excision
 
Estimate of reduction in tumor volume (necrotic cells:tumor cells) at excision*
 
Abscopal effect as determined by
 

	
clinical and histological clearance of nontreated lesions at excision
 
 
• Physician Global Assessment (PGA)
 

Part 2 (Cohorts 1 and 2)	
Primary Objectives	Endpoints

 
• To determine the optimal regimen for dosing 8 mg of VP-315 based on safety and tolerability
 
	
 
• Treatment-related AEs; treatment-related serious adverse events (SAEs); discontinuations due to AEs; occurrence of TRAEs of special interest
 
• CRA
 

Secondary Objectives	Endpoints

 
• To evaluate the antitumor efficacy of VP- 315
 
	
 
• Clinical clearance of treated lesion at excision as determined by visual assessment (no residual tumor seen on visual inspection)
 
• Histological clearance of treated lesion(s) at excision
 
• Abscopal effect as determined by clinical and histological clearance of nontreated lesions at excision if nontreated lesions exist
 
• Estimate of remaining tumor volume (necrotic cells:tumor cells) at excision
 
• Estimate of reduction in tumor volume (necrotic cells:tumor cells) at excision*
 
• PGA
 

Exploratory Objectives	Endpoints

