## **9.5. Cutaneous Reaction Assessment**

A summary of the cutaneous reaction assessments (CRAs) will be provided using the safety population. The number and percentage of subjects falling into each severity category (None (1), Mild (2), Moderate (3), Severe (4), Not Applicable (5)) for reactions of Erythema, Induration, Swelling, Blister Formation, Desquamation, Erosion, Ulceration, and Necrosis will be provided in the summary.

The summary will present reaction within scheduled visit (W1D2, W1D3, W1 Safety Assessment, W2D1, W2D2, W2D3, W2 Safety Assessment, Limited Safety Assessment, EOT, EOS 1 Week Post-excision, EOS 2 Weeks Post-excision) within lesion (TL1, TL2, NTL1, NTL2, NTL3).

A separate listing will be provided for CRAs using the safety population, and this listing will include whether a CRA was Performed (Yes, No), Visit, Date Assessment Performed, and reaction assessments as described above.

A separate listing will also be provided for Photo Assessment using the safety population, and this listing will include Visit, Lesion Photos Taken (Yes, No), Date and Time of Photos, and Photos Uploaded (Yes, No).

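### The CRA summary has no pre-treatment reference: the protocol contradicts itself on a W1D1 assessment, and SAP 9.5 starts at W1D2 without a baseline row

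*Protocol*

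**What the plan says.** The CRA is listed under the primary objective for Part 1, for Part 2 Cohorts 1 and 2, and for Part 2 Cohorts 4 and 5 (Protocol Section 3, SAP Section 2).

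On timing, the protocol gives two accounts.

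- Protocol 8.4.6: "A CRA will be performed prior to injection at all visits after W1D1".
- Table 8-1, footnote m: "Physician's Global Assessment and Cutaneous Reaction Assessment will be performed prior to injection at all visits after Week 1 Day 1". The table has no Screening mark for the CRA.
- Protocol 8.2: "The CRA and PGA will be performed by the investigator or trained personnel at each treatment visit".
- Protocol 8.5.2: "Prior to each treatment, each safety visit, prior to excision and EOS, the treatment site", together with other followed lesions, "will be photographed, and assessed for the CRA".

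The form in Appendix 1 asks for an absolute grade: "Evaluate the tissue condition at the treatment site for the presence and severity of each of the following cutaneous reactions". A note below it sends every reaction graded mild or worse to the adverse event page.

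For the analysis, SAP 9.5 states: "The summary will present reaction within scheduled visit (W1D2, W1D3, W1 Safety Assessment", and continues through the later visits. Results are shown separately for TL1, TL2 and up to three nontarget lesions. There is no Screening, Baseline or W1D1 row and no change from baseline. Protocol 11.5.2 likewise plans only counts and percentages by severity, reaction type and visit.

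**The concern.** The CRA grades what is on the skin, not what has changed. Every target lesion is a tumour with a punch or shave biopsy taken within 90 days of W1D1. Protocol 5.4 sets no minimum interval between biopsy and first injection, and punch sites are sutured (Protocol 8.1). Some erythema, induration, erosion or ulceration before dosing is plausible.

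There is no control arm, so a pre-dose grade on the same lesion is the natural reference. Without it, the table mixes signs that were already there with signs that the injection produced. This bears on an endpoint under the primary objective, and in Cohorts 4 and 5 that objective is meant to inform a pivotal design. Protocol 8.4.6 also makes CRA results an input to the evaluation of necrosis and DLTs.

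**Working it through.** 1. Is there a W1D1 CRA? Protocol 8.4.6 and footnote m exclude it. Protocol 8.5.2 includes it, because the W1D1 injection is a treatment and the CRA is tied to the time before each treatment. Protocol 8.2 also includes it if W1D1 counts as a treatment visit, but this is weaker evidence. That sentence pairs the CRA with the PGA, an improvement score that cannot be given before any treatment. The same pairing appears in footnote m, where a start after W1D1 suits the PGA but not an absolute grade such as the CRA. The documents do not settle what sites did.

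2. Would the SAP use a W1D1 CRA if it existed? No. The visit list in SAP 9.5 begins at W1D2, and SAP Section 14 does not list this as a departure from the protocol. By contrast, SAP 9.2, 9.3 and 9.4 give laboratory values, vital signs and ECG both a baseline and a change from baseline.

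3. Which lesions are affected? Mainly TL1. Treatment of TL2 starts in Week 2 at the earliest, so CRAs of TL2 from W1D2 up to the W2D1 injection precede its own first injection. They appear in the same visit rows, however, and nothing marks them as pre-treatment. SAP 5.5 defines baseline relative to the first injection of study treatment, so it would not pick them out either. Nontarget lesions are biopsied but not injected, and can serve as a reference within the subject. SAP Section 8 notes that not every subject has lesions beyond TL1.

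4. What happens on the adverse event route? Appendix 1 asks for an entry for any mild or worse reaction, without comparison to pre-treatment status. Under SAP 9.1, an event counts as treatment-emergent if it began or got worse once treatment had started, and also if an incomplete onset date leaves this undetermined. A sign first graded at W1D2 has no earlier CRA grade against which to judge onset or worsening. Under Protocol 10.1.1, treatment-related status further needs the investigator's judgement of causality.

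5. How large could the effect be? The plan gives no figure to reproduce. The following is illustration only. Let p0 be the assumed share of TL1 with a given sign before dosing, still present at the visit, and p1 the true share with that sign caused by the drug. Assuming independence:

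apparent rate = 1 − (1 − p0)(1 − p1), so the excess is p0(1 − p1).

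| p0 | Expected TL1 with sign, of 82 in Part 2 (82 × p0) | Of 36 in Cohort 4 (36 × p0) | Apparent rate if p1 = 30% | Apparent rate if p1 = 90% |
|---|---|---|---|---|
| 5% | 4.1 | 1.8 | 33.5% | 90.5% |
| 10% | 8.2 | 3.6 | 37% | 91% |
| 20% | 16.4 | 7.2 | 44% | 92% |
| 40% | 32.8 | 14.4 | 58% | 94% |

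For example, with p0 = 40% and p1 = 30%: 1 − 0.60 × 0.70 = 0.58. The cohort sizes are those in SAP Section 3.

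The share of lesions showing the sign only because it was already there is p0(1 − p1) divided by the apparent rate. At p1 = 30% it runs from 0.035/0.335 = 10% (p0 = 5%) to 0.28/0.58 = 48% (p0 = 40%). At p1 = 90% it runs from 0.005/0.905 = 0.6% to 0.04/0.94 = 4%. So the prevalence of prior signs is not the share of reactions that are spurious.

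**The case against.** A reader might infer that no pre-injection assessment exists at all. The documents do not support that: Protocol 8.5.2 calls for one, and the Table 8-1 treatment column covers Days 1 to 3. What can be shown is a contradiction, plus a SAP table that omits W1D1 in either case.

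A reader might also infer that pre-existing signs are counted as drug reactions. That is too strong. The CRA table counts signs without attributing them. On the adverse event side, several safeguards stand: the requirement of onset or worsening, the rule in Protocol 10.1.1 that a pre-existing condition counts only if it worsens, the causality judgement, and the screening-relatedness question in Protocol 10.1.2. Protocol 8.4.6 also says that these reactions are collected separately from adverse reactions, which sits awkwardly with the note in Appendix 1. Misattribution is possible, not automatic.

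Other records exist. Lesions are photographed before each treatment, and a limited skin examination is done predose. These help clinically, but they carry no CRA grade. SAP 9.5 lists only whether photographs were taken and uploaded, and SAP 9.6 gives examinations in listings without tables.

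The lack of a CRA baseline does not breach SAP 5.5, since no change from baseline is planned for the CRA. Nor is an effect shown on the moderate-or-worse adverse event summaries or on the Grade 2 criteria for DLTs and TRAE SIs, if prior signs are mostly mild.

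Finally, the trial is descriptive, and the SAP, dated 6 September 2024, gives exact cohort sizes, which suggests that enrolment is complete. That limits which remedies are still open. It does not remove the gap in the table.

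**Conclusion.** The point holds for the CRA summary. The protocol is inconsistent on whether the CRA is done before the first injection, and SAP 9.5 provides no pre-treatment reference either way. Signs already present in TL1 cannot be separated from new reactions in that table, and some may also reach the adverse event summaries.

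The size is unknown. The documents give no prevalence of prior signs, so the 5–40% range is an assumption, as are independence and persistence of the sign to the visit. On that basis the distortion could be large for reactions that the drug causes in a minority of lesions (30% appearing as 33.5–58%) and is small for near-universal ones (90% appearing as 90.5–94%). It concerns TL1 chiefly. This is a worthwhile, inexpensive improvement to how a primary-objective endpoint can be read. It does not show that the reported reactions are spurious.

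**What to change.** In the protocol, reconcile 8.2, 8.4.6, 8.5.2 and footnote m so that the CRA form is completed before the first injection on W1D1, separately from the PGA.

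In SAP 9.5, before database lock, first establish whether W1D1 CRAs were collected.

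- If they were, define a baseline for each lesion: W1D1 for TL1 and nontarget lesions, and for TL2 the last CRA before its own first injection. Add it as a row, and tabulate reactions worse than baseline alongside the absolute grades.
- If they were not, state that TL1 CRA rates include any signs present before dosing. Use the predose W1D1 photographs and skin examinations, and the uninjected nontarget lesions, as supportive references. The lesion-specific baseline for TL2 can still be used where TL2 was graded before its first injection.

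The cost is one more completion of an existing form at an existing visit, and one more display. If the data are already in, only the SAP part applies. Made after lock, it would be post hoc under SAP 5.2.
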